4.6.1.6 Analysis of FACIT

The absolute value, change and percent change from baseline for Functional Assessment of Chronic Illness Therapy (FACIT) Fatigue scale at weeks 4, 12, 24, 36 and 48 will be summarized as a continuous variable by treatment group and visit, percent change from baseline will also be plotted.

4.6.1.7 Analysis of CRP/ESR

The absolute value, change and percent change from baseline for CRP/ESR at weeks 4, 12, 24, 36 and 48 will be summarized by descriptive statistics as a continuous variable by visit and treatment group, percent change from baseline will be plotted.

4.6.1.8 Analysis of rheumatoid factor and anti-CPP antibodies

The number of patients having positive and negative values, and for positive cases a continuous value for rheumatoid factor and anti-CPP at baseline, Week 24 and 48 (for last two also change from baseline) will be summarized by descriptive statistics by treatment group.

4.6.2 Safety evaluation

All safety evaluations will be performed on the Safety set.

4.6.2.1 Adverse Event

AEs will be summarized by presenting the number and percentage of patients having any AE, by SOC and PT.

In addition, the number of events will also be presented for any AE, by primary SOC and for each PT. The average rate of adverse events will also be calculated as the number of events divided by the total number of years of exposure.

Missing and /or incomplete dates for AEs are imputed in a manner resulting in the earliest onset during the study period (see [Appendix 1](#) for details), additionally taking into account that the start date should not be after the stop date. The maximum of the earliest possible start date and the date of first administration of investigational study medication will be imputed for missing dates. If the end date is prior to the date of first administration of investigational study medication then the AE is not considered as a TEAE.

AE summary will be provided for all study periods by treatment groups and for the entire study separately. Following data will be summarized in the overall AE summary presentation.

Total number of TEAEs, patients with at least one TEAE, at least one SAE, at least one treatment related TEAE, at least one severe TEAE, at least one treatment related SAE, patients who discontinued the study due to TEAE, patients requiring study drug interruption and number of patients who died.

4.6.2.1.1 Summary of AEs by severity

Severity is classified as mild/moderate/severe (increasing severity). Treatment emergent AEs starting after the first dose of study medication with a missing severity will be classified as severe. If a patient reports a TEAE more than once within that SOC/PT, the TEAE with the highest severity will be presented.

4.6.2.1.2 Summary of study treatment related AEs.

Relationship, as indicated by the investigator, is classed as suspected/not suspected/not applicable (before study drug administration). A related TEAE is defined as a TEAE with a relationship to study medication as “suspected” to study medication. Treatment emergent AEs with a missing relationship to study medication will be regarded as “suspected” to study medication. If a patient reports the same TEAE more than once within that SOC/PT, the TEAE with the worst case relationship to study medication will be presented.

4.6.2.1.3 Summary of AEs of special interest

Selected AEs, considered under the heading of potential and identified risks will be presented under summary of AEs of special interest. Definition of an AE as an AE of special interest is given in [Appendix 3](#).

In addition separate summaries will be provided for death, serious AEs (SAEs), other significant AEs leading to discontinuation by treatment group and overall.

These summaries will be presented separately for all study periods by treatment group and overall.

4.6.2.1.4 Injection site reactions

All AEs marked as ISRs in the eCRF will be summarized by presenting the number and percentage of patients having any ISR and by signs/symptoms. Injection site reactions will also be presented by severity. In addition, the number of events for ISRs will also be presented overall for any ISR and by sign/symptom. If a patient reported more than one identical ISR, the ISR with the greatest severity will be presented. If a patient reported more than one identical ISR, the patient will be counted only once with the greatest severity. If the severity is missing for an ISR, severity will be classified as severe. ISRs will be presented separately for all study periods by treatment groups and overall. In addition, ISRs which are considered SAEs will be presented as counts and percentages separately.

4.6.2.2 Laboratory data

Results from the central laboratory will be included in the reporting of this study. The summaries presenting a number of patients with new notable abnormalities (according to the protocol), as well as shift tables by toxicity grades will be presented for hematology and serum chemistry by treatment group for each Study Period. Standard units will be used for presentation. Box plots of parameters of interest will be done by treatment and study period. The laboratory results below the LLOQ will be imputed as zero, the laboratory results above the upper detection limit will be imputed as upper detection limit.

All laboratory data (including urinalysis) will be listed. Notable abnormalities will be listed in addition.

4.6.2.3 Vital Signs

Vital signs measurement includes blood pressure (systolic and diastolic), pulse and temperature. The summary presenting a number of patients with new notable abnormalities (according to normal range criteria) will be presented by treatment group for each study period. All information collected will be listed. Notable abnormalities will be listed in addition.

4.6.2.4 ECG

All ECG results will be shown in a listing.

4.6.2.5 Physical examination

Physical examination results will be shown in listing.

4.6.3 Immunogenicity

Summary statistics (frequency and percentage) by treatment group and overall and sampling day will be provided for the percent of patients with ADA formation at baseline, weeks 2, 4, 12, 24, 36 and 48 or End of Study visit.

ADA positive patients at baseline will not be considered for the analysis of immunogenicity (development of ADA) at post-baseline assessments. A patient is considered as ADA positive during the study if the patient had at least one post baseline ADA positive sample otherwise the patient is regarded as ADA negative. Note this will also include any unscheduled visits during the Study Period.

A transient ADA response occurs where a post baseline positive ADA response occurs but is followed by a negative ADA response during the study.

The titer and the concentration of confirmed positive results will be reported. In addition, confirmed positive ADA samples will be analyzed for their neutralization potential in a neutralizing antibody (NAb) assay.

The incidence of ADA positive patients, patients with a transient response and patients with neutralizing ADAs will be summarized by treatment arms.

All ADA data will be listed (including titer and concentration).

The SAF will be used to summarize the data.

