### **Study period 2: Week 24 - Week 48**

- To evaluate clinical safety in patients treated continuously with GP2017 and in patients treated with GP2017 after switch from US-licensed Humira® as assessed by changes in vital signs, clinical laboratory parameters and incidence and severity of AE
- To evaluate incidence and severity of injection site reactions (ISRs) in patients treated continuously with GP2017 and in patients treated with GP2017 after switch from US-licensed Humira®
- To evaluate immunogenicity as determined by measuring the incidence of ADA formation against adalimumab in patients treated continuously with GP2017 and in patients treated with GP2017 after switch from US-licensed Humira®
- To evaluate efficacy in patients treated continuously with GP2017 and in patients treated with GP2017 after switch from US-licensed Humira® as assessed by DAS28-CRP, DAS28-ESR score changes from Week 24 at Week 48 and ACR20/50/70 responses at Week 48
- To compare Health Assessment Questionnaire-Disability Index (HAQ-DI) changes from Week 24 at Week 48 in patients treated continuously with GP2017 and in patients treated with GP2017 after switch from US-licensed Humira®
- To compare the proportion of patients treated continuously with GP2017 and patients treated with GP2017 after switch from US-licensed Humira® achieving HAQ-DI score  $\leq 0.5$  at Week 48
- To compare Functional Assessment of Chronic Illness Therapy (FACIT) Fatigue scale changes from Week 24 at Week 48 in patients treated continuously with GP2017 and in patients treated with GP2017 after switch from US-licensed Humira®

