- Immunogenicity as determined by measuring the incidence of ADA formation against adalimumab in patients treated continuously with GP2017 and in patients treated with GP2017 after switch from US-licensed Humira®

Objectives	Endpoints
	
• Efficacy in patients treated continuously with GP2017 and in patients treated with GP2017 after switch from US-licensed Humira® as assessed by DAS28-CRP, DAS28-ESR score changes from Week 24 at Week 48 and ACR20/50/70 responses at Week 48• Health Assessment Questionnaire-Disability Index (HAQ-DI) changes from Week 24 at Week 48 in patients treated continuously with GP2017 and in patients treated with GP2017 after switch from US-licensed Humira®• Proportion of patients treated continuously with GP2017 and patients treated with GP2017 after switch from US-licensed Humira® achieving HAQ-DI score ≤0.5 at Week 48• Functional Assessment of Chronic Illness Therapy (FACIT) Fatigue scale changes from Week 24 at Week 48 in patients treated continuously with GP2017 and in patients treated with GP2017 after switch from US-licensed Humira®

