4.1 General considerations

4.1.1 Baseline definition

Unless stated otherwise, baseline is defined as the pre-dose assessment taken at Visit 2. For FACIT, HAQ-DI and Tender/swollen joints assessments baseline is defined on the questionnaire level, not on an individual measurements level.

For quantitative measurements, change and percent change from baseline will be calculated as:

- Change from baseline = Post-baseline value – Baseline value
- Percent change from baseline = $100\% * (\text{Post-baseline value} - \text{Baseline value}) / \text{Baseline value}$ for baseline values greater than 0.

Changes from baseline will only be summarized for patients having both baseline and post baseline values.

For the changes from Week 24 at Week 48 in terms of DAS28-CRP, DAS28-ESR, HAQ-DI score, and FACIT Fatigue scale, the nominal Week 24 and Week 48 visit values will be used.

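### SAP 4.6.3 defines no measure of ADA that first appear in Study Period 2, so antibodies formed in Study Period 1 count toward the post-switch incidence in both groups

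*SAP*

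**What the plan says.** SAP Table 2-1 (section 2.2) lists as an SP2 endpoint "Immunogenicity as determined by measuring the incidence of ADA formation against adalimumab in patients treated continuously with GP2017", and likewise in patients switched from Humira. Protocol 2.2 words the objective in the same way: "To evaluate immunogenicity as determined by measuring the incidence of ADA formation against adalimumab in patients treated continuously with GP2017".

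SAP 4.6.3 then gives the analysis:

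- Patient-level status: "A patient is considered as ADA positive during the study if the patient had at least one post baseline ADA positive sample"; every other patient is classed as negative.
- Exclusion: "ADA positive patients at baseline will not be considered for the analysis of immunogenicity (development of ADA) at post-baseline assessments".
- Unscheduled samples: "Note this will also include any unscheduled visits during the Study Period".
- By-visit percentages at baseline and Weeks 2, 4, 12, 24, 36 and 48 (or End of Study), by treatment group, on the safety set, plus listings of all ADA data with titer and concentration.

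The reference point comes from SAP 4.1.1: "Unless stated otherwise, baseline is defined as the pre-dose assessment taken at Visit 2". No other reference is stated for ADA. The SP2 safety set (SAP 2.7.3) takes all SP1 safety-set patients who enter SP2 and are dosed there, so patients who became ADA positive in SP1 stay in it.

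**The concern.** The SP2 aim includes the effect on immunogenicity of switching from Humira to GP2017. That calls for a count of antibodies that appear after the switch. The only patient-level rule looks back to Visit 2 and removes only patients already positive then. A patient who becomes positive at Week 4 and stays positive can therefore be reported under SP2 ADA formation, although the antibody predates SP2. This applies to patients continuing GP2017 as well as to switched patients.

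The gap is particular to ADA. SAP 4.1.1 gives DAS28, HAQ-DI and FACIT an explicit Week 24 reference for SP2 change, and SAP 4.1.2 assigns adverse events and medications to SP1 or SP2. ADA status has neither. At stake is whether the report can show, from a measure defined before unblinding, how many patients formed ADA for the first time after Week 24 in each group.

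**Working it through.** **Plan's own figures.** The documents give no ADA rate, no SP2 group size, and no margin or power for immunogenicity, so there is no stated figure to reproduce. For scale, 154 per arm with 20% loss (protocol 5.2 and 4) gives 154 × 0.8 = 123.2, about 123 per arm. Week 24 non-responders also stop, so SP2 could be smaller; 90 per arm is used as an alternative assumption.

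**Sample window.** SAP 4.1.2 assigns an assessment on the SP2 start day to SP1. The Week 24 pre-dose sample is therefore an SP1 sample, and the scheduled SP2 samples are Weeks 36 and 48.

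**Notation (all values assumed).** p = share of SP2 patients positive at any post-baseline SP1 sample. q0, q1 = new onset in SP2 among SP1 negatives, continued and switched. f = share of SP1 positives still positive in SP2.

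- Reading A, all samples since Visit 2: rate = p + (1 − p)q.
- Reading B, SP2 samples only, SP1 positives kept: rate = f·p + (1 − p)q.
- New onset among SP1 negatives: rate = q.

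With p (and f) equal in both groups, the A and B differences are both (1 − p)(q1 − q0), because the carry-over term cancels. The ratio is pulled toward 1.

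**Equal SP1 rates.** q0 = 5%, q1 = 15%, f = 0.7. New onset itself is 5% vs 15%: 10 points, ratio 3.0.

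| p | A: continued vs switched | A ratio | B: continued vs switched | B ratio | Difference (A and B) | SP1 negatives of 123 |
|---|---|---|---|---|---|---|
| 10% | 14.5% vs 23.5% | 1.62 | 11.5% vs 20.5% | 1.78 | 9 points | 111 |
| 20% | 24.0% vs 32.0% | 1.33 | 18.0% vs 26.0% | 1.44 | 8 points | 98 |
| 30% | 33.5% vs 40.5% | 1.21 | 24.5% vs 31.5% | 1.29 | 7 points | 86 |
| 40% | 43.0% vs 49.0% | 1.14 | 31.0% vs 37.0% | 1.19 | 6 points | 74 |
| 50% | 52.5% vs 57.5% | 1.10 | 37.5% vs 42.5% | 1.13 | 5 points | 62 |

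For example, at p = 30% under A: 0.30 + 0.70 × 0.05 = 0.335 and 0.30 + 0.70 × 0.15 = 0.405. The rates and ratios do not depend on group size. With 90 per arm, the SP1 negatives fall from 81 at p = 10% to 45 at p = 50%.

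**Unequal SP1 rates, reading A.**

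- No switch effect (5% in both), SP1 rates 30% GP2017 and 40% Humira: (0.40 + 0.60 × 0.05) − (0.30 + 0.70 × 0.05) = 0.430 − 0.335 = +9.5 points, all of it carry-over.
- True 5% vs 15%, SP1 rates 40% GP2017 and 30% Humira: (0.30 + 0.70 × 0.15) − (0.40 + 0.60 × 0.05) = 0.405 − 0.430 = −2.5 points, so the sign reverses.

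Entry into SP2 depends on Week 24 response, so randomization does not guarantee equal SP1 rates among those who enter.

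**The case against.** The quoted rule speaks of status during the study and is not labelled an SP2 rule. SAP 2.1.2 plans separate SP1, SP2 and overall tables, and SAP 2.7 adds an analysis of the entire study; the rule fits that analysis naturally. The note on unscheduled visits refers to the Study Period, SAP 4.1.2 separates the periods, and the transient-response definition in SAP 2.3.2.3 mentions the end of Treatment Period 1. A reader might infer that the SAP instructs SP2 tables to count every positive since Visit 2. It does not say so; that is one literal reading, and this part of the objection stands. It does not close the gap. If the rule serves only the entire-study tables, SP2 has no patient-level rule. If only SP2 samples count, persisting SP1 antibodies still enter.

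The by-visit rates at Weeks 24, 36 and 48 show the net change after the switch, and the listings allow each new positive to be found. This is real but partial information. By-visit percentages mix persistent and new positives, and gains and losses can cancel. A definition drawn from the listings would be made after unblinding.

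SP2 ADA is to be evaluated descriptively, with no planned test. That also stands, so the working reports rates and ratios and makes no power argument.

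Classing a patient with no post-baseline sample as negative matters little in SP2, since patients reach it after scheduled samples at Weeks 2, 4, 12 and 24. An evaluable sample after the first SP2 dose is still worth requiring.

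**Conclusion.** The point holds as a missing definition. The SAP has no measure of ADA first appearing in SP2, and under either reading of its one patient-level rule some or all SP1 seroconverters count toward the SP2 incidence in both groups.

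Three stronger conclusions are tempting and are not supported. One is that a switch signal is necessarily diluted: that needs similar SP1 rates, and otherwise the distortion can go either way. Another is that only antibodies formed under Humira are carried over: those formed under GP2017 in SP1 are too. The third is that the trial cannot answer its switch question: the data will exist, and what is missing is the pre-specified summary.

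The factor 1 − p is exact under the literal reading with equal SP1 rates. Every percentage in the illustration is an assumption, because the documents supply no ADA rate. Across p from 10% to 50%, an assumed new-onset ratio of 3.0 would be reported as 1.62 down to 1.10. This is a secondary, descriptive endpoint; the primary efficacy conclusion is untouched.

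**What to change.** In SAP 4.6.3, state which samples determine ADA status in the SP2 tables, and add one descriptive table by SP2 group:

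- **Denominator:** SP2 safety-set patients who are ADA negative in all samples up to and including the Week 24 pre-dose sample and have at least one evaluable later sample.
- **Numerator:** at least one confirmed positive sample after the first SP2 dose (Week 36, Week 48, End of Study or unscheduled).
- **New neutralizing ADA:** presented in the same way.
- **SP1-positive patients:** shown separately, with persistence and titer change.

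The existing rule can remain for the entire-study tables if labelled as such. The cost is a short definition and one table; the sampling in protocol Table 6-4 and SAP Table 2-5 already covers it. The downside is a smaller at-risk denominator: in the illustration, about 111 down to 62 of 123 per arm.

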## 4 Population

The study population will consist of male and female patients who are at least 18 years of age with active moderate to severe RA who failed previous treatment with MTX with or without other DMARDs. RA diagnosis must be established according to the ACR 1987 or revised ACR/EULAR 2010 criteria ([Aletaha et al 2010](#)) with a disease duration of  $\geq 6$  months, and with disease activity defined as DAS28-CRP score  $\geq 3.2$  at screening. Patients must be on a stable MTX dose for at least 4 weeks prior to baseline (randomization) and should continue on this stable dose throughout the study. The selection of the population is based on the EULAR/ACR recommendations ([Smolen et al 2014\(a\)](#)) for management of RA and CHMP draft guideline on clinical investigation of medicinal products other than NSAIDs for treatment of RA.

The study is planned to randomize approximately 308 patients in approximately 110 centers worldwide. Patients that drop out after they have been randomized will not be replaced. A screen failure rate of 30% and a post-randomization dropout rate of 20% are anticipated. If the screen failure rate appears to be higher than expected, more patients will be screened. Screening will stop when the target number of randomized patients is anticipated. All patients in screening at that point of time will remain eligible for randomization.

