#### **6.5.6 Immunogenicity and adalimumab trough levels**

As with all therapeutic proteins, there is a potential for immunogenicity and the emergence of antibodies to human recombinant proteins is well documented. Antibodies directed against a therapeutic agent may have neutralizing activity and interfere with the efficacy of the treatment. For safety reasons, screening for anti-adalimumab antibodies (ADA) has been included in this study.

Immunogenicity will be assessed by measuring anti-adalimumab antibody levels in serum of all subjects. During the study, immunogenicity will be assessed at:

- baseline, Week 2, Week 4, Week 12, Week 24, Week 36 and Week 48 (at Visits 2, 3, 4, 8, 14, 15, and 16)

For details on blood collection time points and sample information please refer to [Table 6-4](#).

To support the evaluation of immunogenicity, adalimumab trough levels will be determined at every time-point when blood samples for ADA assessment are taken. Thereby, the drug tolerance level of the ADA method (which will be determined during method validation) can be compared with the determined drug levels. For details on blood collection time points and sample information please refer to [Table 6-5](#).

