2.1.2 General considerations

Raw data listings, summary tables, figures and statistical tests will be generated using the SAS® Version 9.4 or higher.

All clinical data, including laboratory, immunogenicity, and pharmacokinetics data will be provided as raw data from an external database. CDISC SDTM 3.1.2 amendment 1 compliant SAS® datasets will be prepared. The final SDTM files will also include variables indicating the actual and planned treatment assigned.

Coding of corresponding data (e.g. by Medical Dictionary for Regulatory Activities [MedDRA] or World Health Organization [WHO]-drug dictionary), and ATC coding is included in the SDTM datasets.

Appropriate SAS® programs will be prepared and validated according to standard operating procedures.

The following descriptive statistics will be shown in summary tables:

- Continuous variables: n (number of patients with evaluable data), mean, standard deviation (SD), minimum, median, maximum. Quartiles will be presented as appropriate.
- Categorical variables: Count and percentage of each category. A row denoted “Missing” will be included in count tabulations where necessary to account for dropouts and missing values. Unless otherwise specified, the denominator for all percentages will be the number of patients in the treatment group within the analysis set of interest. Percentages will not be provided if the number is zero.

The same number of decimal places as in the raw data will be presented when reporting minimum and maximum, 1 more decimal place than in the raw data will be presented when reporting mean, median and quartiles, and 2 more decimal places than in the raw data will be presented when reporting SD and SE.

For the derived variables, appropriate precision should be provided in CSR appendix data listing. E.g., for the DAS28-CRP and DAS28-ESR, 2 decimal places will be kept in the data listing, the decimal places of the descriptive statistics will then follow the rules above accordingly (i.e., treat raw data as 2 decimal places).

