2.7.3 Safety set (SAF)

Study Period 1 Safety set (SP1 SAF): consists of all subjects who received at least one dose of IMP, whether randomized or not. Subjects will be analyzed according to the treatment received.

Study Period 2 Safety set (SP2 SAF): The SP2 SAF set includes all SP1 SAF patients entering Study Period 2 who received at least one dose of IMP in Study Period 2.

3 Changes to planned analyses

Based on the study protocol Section 2.2, the efficacy evaluation of Study Period 2 includes calculating the changes from Week 24 at Week 48 for the following variables: DAS28-CRP, DAS28-ESR, HAQ-DI score, and FACIT fatigue score. In addition to changes from Week 24 at Week 48, the changes from baseline (i.e., randomization) at all applicable Study Period 2 visits will also be calculated and analyzed for above variables.

In addition to the study protocol defined objectives for SP1 and SP2 separately, the entire study data (i.e., from the randomization up to Week 48) will also be analyzed.

The SAP section “Power for analysis of key secondary endpoint”, more detailed information than in the study protocol are provided.

The protocol specifies no imputation for missing components of the DAS28-CRP score, because it was assumed that joint surgery would not occur. In accordance with general practice, the joints which not assessable throughout the study will be considered as not having tenderness or swelling (see Section 2.3.1.1).

4 Statistical analyses

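### SAP 4.6.3 makes ADA negative the default, with no evaluable denominator and no drug-tolerance rule, so reported ADA incidence can be understated

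*SAP*

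**What the plan says.** **Patient status.** SAP 4.6.3 makes a patient ADA positive if any post-baseline sample, unscheduled ones included, is positive; "otherwise the patient is regarded as ADA negative". There is no third category. The only stated exclusion is that "ADA positive patients at baseline will not be considered for the analysis of immunogenicity" at post-baseline assessments.

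**Analysis set and denominator.** SAP 4.6.3 states: "The SAF will be used to summarize the data". Under SAP 2.7.3 the Study Period 1 safety set "consists of all subjects who received at least one dose of IMP, whether randomized or not". SAP 2.7 also assigns that set to the entire-study analyses. SAP 4.6.3 names no denominator. The general rule in SAP 2.1.2, unless specified otherwise, is that "the denominator for all percentages will be the number of patients in the treatment group within the analysis set of interest". The same paragraph provides a 'Missing' row, which "will be included in count tabulations where necessary to account for dropouts and missing values". SAP 4.7, on missing data, points only to the joint-count and partial-date rules.

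**Sample status.** Under SAP 2.3.2.3 and Protocol 6.5.6.2, a sample below the screening cut-point, or not confirmed, is negative. The drug level plays no part.

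**Trough levels.** Protocol 6.5.6 has a trough drawn with every ADA sample so that the assay's drug tolerance "can be compared with the determined drug levels"; SAP 2.3.2.4 repeats this. SAP 4.6.4 then plans descriptive statistics by treatment group and overall, and a listing of concentrations beside ADA results.

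**The concern.** These rules can turn an unknown ADA status into a negative one, or dilute a percentage with patients who were not sampled. None of them works in the other direction. ADA formation is a stated objective in both study periods (Protocol 2.2), and Protocol 3.6 treats its assessment as essential.

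If both arms are affected equally, both rates fall and the absolute difference shrinks, which favours a conclusion of similarity. If loss or masking differs between arms, a difference can appear or disappear. ADA status also splits sensitivity analyses of the primary and key secondary endpoints (SAP 4.5 and 4.6.1.1).

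**Working it through.** There is no plan figure to reproduce. The documents give no expected ADA incidence, no expected number of patients without samples and no tolerance level. All rates below are assumptions, except the 154 patients per arm from Protocol 5.2.

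**1. By-visit percentages**

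Printed % = p × s, where p is the proportion positive among those sampled at the visit and s is the share of the safety set sampled.

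- Patients without at least a moderate DAS28-CRP response leave at Week 24 by design (Protocol 5.2), and other patients drop out. In entire-study tables on the Study Period 1 safety set, all of them remain in the Week 36 and Week 48 denominators.
- With p = 40%: 0.40 × 0.60 = 24%, and 0.40 × 0.65 = 26%.
- Study Period 2 tables use a set limited to patients dosed in that period, so Week 24 non-responders are not in them. Only later losses dilute those tables.

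**2. Patients with no post-baseline sample**

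Reported % = p × (1 − m), where m is the share never sampled after baseline, assumed to have the same true rate as the rest.

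- With p = 30%: m = 1% gives 0.30 × 0.99 = 29.7%; m = 5% gives 0.30 × 0.95 = 28.5%; m = 10% gives 27.0%.
- In counts, with 8 of 154 unsampled and 44 positive: 44/146 = 30.1% among those sampled, against 44/154 = 28.6% under the SAP rule.
- If the arms differ, m = 2% and m = 8% print equal true rates of 30% as 0.30 × 0.98 = 29.4% and 0.30 × 0.92 = 27.6%.

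**3. Drug tolerance**

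Reported % = p × (1 − f), where f is the share of truly positive patients whose samples all read negative because of drug.

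- With p = 30%: f = 10% gives 27%, f = 30% gives 21%, and f = 50% gives 15%.
- If the tolerance exceeds the observed troughs, f = 0 and nothing changes.
- Only negative results are in question. A sample above tolerance that screens and confirms positive stays positive.

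**4. Analyses by ADA status**

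These repeat the primary and key secondary analyses, which are run on the Week 12 and Study Period 1 per-protocol sets. SAP 2.7.2 requires completion of Week 12 or Week 24 respectively, and both are ADA sampling visits. Patients never sampled are therefore essentially absent, and route 2 hardly matters there. Route 3 does: masked positives would sit in the negative subgroup.

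**The case against.** The strongest reply is that ADA reporting is descriptive, with no test or margin, and that the pieces needed for a careful reading are already planned. The 'Missing' row lets a reader recompute a by-visit rate, and the listing puts each trough beside its ADA result. This is fair as to severity. It does not change the printed percentage, and a patient already defined as negative will not appear as missing. A listing is also not an analysis by arm.

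The group never sampled should be small. Sampling starts at Week 2, unscheduled samples count, and early leavers are asked to attend the Visit 16 assessments (Protocol 6), although they may refuse. This stands, and it is why route 2 is rated small.

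Early End of Study visits can be mapped to scheduled visits (SAP 2.1.2 and 4.1.4). SAP 4.6.3 may also mean to pool Week 48 with the End of Study visit. Either would soften route 1 at some visits. Week 36 would still be exposed, and the pooling should be stated.

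A reader might infer several stronger points that the documents do not support:

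- **Baseline-positive patients stay in the denominator.** SAP 4.6.3 most naturally removes them.
- **A 40% rate prints as 32% at Week 24.** This takes 0.40 × 0.80 from the protocol's statement that "a post-randomization dropout rate of 20% are anticipated". That figure carries no time point, and the reading ignores End of Study mapping.
- **Rising troughs show that interference roughly doubles as antibodies develop.** A relative rise in concentration says nothing about interference without the tolerance level, and the documents give no timing for ADA development.

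**Conclusion.** The point holds as a statement of what can happen. As written, SAP 4.6.3 with SAP 2.1.2 can understate ADA incidence; the documents do not show that it will, or by how much.

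- **Route 1** can be the largest with a calculable size: 40% printing as 24-26% at Weeks 36 and 48 of the entire-study tables. It rests on the assumed 40% and on 60-65% still being sampled.
- **Route 2** is probably small: 30% reading 28.5% if 5% are unsampled.
- **Route 3** has unknown size, possibly nil, because the tolerance is not given. It is the only route that bears materially on the analyses by ADA status.

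The change is worth making before unblinding. The primary equivalence test itself is not affected.

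**What to change.** In SAP 4.6.3:

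- (a) Base by-visit ADA percentages on patients with a valid ADA result at that visit. Base patient-level incidence on baseline-negative patients with at least one valid post-baseline result, and show the number of other patients as 'not evaluable', by arm.
- (b) Class a negative sample whose concurrent adalimumab level exceeds the validated tolerance as 'inconclusive'. Report incidence by arm with and without patients whose negative status rests on inconclusive samples.
- (c) Summarise troughs by arm and ADA status.

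The cost is SAP wording and a few more tables. The samples are already collected, and SAP 2.3.2.4 says the tolerance was determined in method validation. The downside is that ADA percentages will come out somewhat higher and some patients will be classed as not evaluable or inconclusive. At Weeks 36 and 48 the rate will describe only patients still in the study, which a footnote should say.
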